To tackle this issue, the Evidence-Based Nursing Center at Fudan University has launched the "Evidence-Based Practice Project for Managing Musculoskeletal Symptoms in Breast Cancer Patients Undergoing Endocrine Therapy from a Multicultural Perspective." This project aims to improve symptom management for breast cancer patients across various cultural backgrounds through the clinical application of scientific evidence, thereby enhancing the quality of nursing care. Based on implementation science, this study explores how to effectively apply and disseminate evidence-based nursing strategies in different regions and cultural environments, fostering cross-cultural healthcare cooperation and advancing the global optimization of breast cancer patient care.

2. Research Objectives (Why)

This study aims to identify best practices for managing musculoskeletal symptoms in breast cancer patients undergoing endocrine therapy within a multicultural context through a multi-center, parallel, randomized controlled implementation study. It also seeks to evaluate the translation and application of scientific evidence across different cultural backgrounds.

The specific objectives are as follows:

2.1 To investigate the current incidence of musculoskeletal symptoms among breast cancer patients undergoing endocrine therapy in Shanghai (China), Dali (Yunnan,

China), and Jakarta (Indonesia), and to assess the knowledge, attitudes, and practices (KAP) of oncology nurses in symptom management in these locations.

2.2 To conduct a multi-center, parallel, randomized controlled study guided by implementation science, evaluating the effectiveness of interventions in managing musculoskeletal symptoms for breast cancer patients undergoing endocrine therapy across different cultural contexts. This study will also validate the translation of scientific evidence in multicultural settings and explore the feasibility and scalability of the interventions across diverse cultural and healthcare systems.

3. Research Design

This study employs a simple randomized controlled trial (RCT) design to assess the effectiveness of musculoskeletal symptom management in breast cancer patients undergoing endocrine therapy from a multicultural perspective.

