3.1 Sample Size

The primary measurement tool for this study is the Western Ontario and McMaster Universities Osteoarthritis Index (WOMAC), used to assess aromatase inhibitor-related musculoskeletal symptoms in breast cancer patients. The sample size estimation is based on effect size and standard deviation data from previous studies, with a significance level of $\alpha=0.05$ and a statistical power of 80%. The calculated effect size is 0.78. Based on these parameters, each group requires 26 patients, with an additional 20% to account for potential attrition, resulting in a total of 33 patients per group.

Each research site will thus recruit 33 patients for both the intervention and control groups.

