3.2 Sampling Method

Patients will be screened and recruited on a consecutive enrollment basis, meaning that all patients meeting the inclusion criteria will be enrolled sequentially during the study period until the predetermined sample size is reached.

Upon enrollment, each patient will undergo a comprehensive baseline assessment, and the research team will ensure that patients understand the study's details and voluntarily sign informed consent forms. After enrollment, patients will be assigned

to either the intervention or control group based on a computer-generated random sequence. The intervention group will receive a management program for musculoskeletal symptoms, while the control group will receive standard care.

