4.2 Intervention Participants (Who)

4.2.1 Target Population

Patients undergoing endocrine therapy after early-stage breast cancer surgery.

- **Inclusion Criteria:**
 - Pathologically confirmed hormone receptor-positive (HR+) breast cancer patients.
 - Aged 18 years or older.
 - Currently receiving aromatase inhibitor therapy (e.g., anastrozole, letrozole, exemestane) for at least 6 months.
 - Reports musculoskeletal symptoms induced by endocrine therapy before enrollment.
 - Capable of understanding the study and willing to sign informed consent.
- **Exclusion Criteria:**
 - Patients with a history of fracture or surgery within the past 6 months.
 - Patients diagnosed with arthritis (e.g., rheumatoid arthritis).
 - Patients diagnosed with osteoporosis according to WHO criteria (T-score \leq -2.5).
 - Patients with recurrent or metastatic breast cancer.
 - Patients with other primary malignancies.
 - Patients with severe heart, brain, liver, or kidney dysfunction, or infectious diseases.

- Patients with severe mental, cognitive, or behavioral disorders that hinder understanding or participation in the study.

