4.3 Intervention and Follow-Up Duration (When)

This study includes a baseline survey, a 3-month intervention period, and a 3-month follow-up period, for a total duration of 6 months.

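### The symptom-frequency half of objective 2.1 cannot be answered from the only patient population the protocol defines, because having symptoms is a condition of entry

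*Protocol*

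**What the plan says.** Section 2 of the protocol lists two specific objectives. The first half of objective 2.1 is "To investigate the current incidence of musculoskeletal symptoms among breast cancer patients undergoing endocrine therapy" in the three cities. Its second half concerns the knowledge, attitudes and practices (KAP) of oncology nurses. Objective 2.2 is the randomised comparison.

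Section 3 describes one design: "This study employs a simple randomized controlled trial (RCT) design". The rules that decide which patients supply data are these:

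- Section 4.2.1, symptom criterion: "Reports musculoskeletal symptoms induced by endocrine therapy before enrollment".
- Section 4.2.1, exposure criterion: "Currently receiving aromatase inhibitor therapy (e.g., anastrozole, letrozole, exemestane) for at least 6 months".
- Section 3.2, recruitment: "all patients meeting the inclusion criteria will be enrolled sequentially during the study period until the predetermined sample size is reached".
- Section 3.2, timing of baseline data: "Upon enrollment, each patient will undergo a comprehensive baseline assessment".
- Section 4.3, timeline: "This study includes a baseline survey, a 3-month intervention period, and a 3-month follow-up period, for a total duration of 6 months".

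No section of the text defines a second patient population, asks for the symptom status of patients who are screened but not enrolled, or gives a denominator or sample size for the frequency part of objective 2.1.

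**The concern.** A frequency needs a denominator that contains people with and without the condition. Here the condition is an entry requirement, so the enrolled cohort supplies a numerator and no independent denominator. A proportion with any symptom computed from enrolled patients would restate the eligibility rule.

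The word incidence adds a second difficulty. New onset can be counted only in people who are free of symptoms at the start, and the criteria admit none. The exposure criterion also narrows the population: the objective speaks of endocrine therapy in general, whereas the trial takes patients established on an aromatase inhibitor.

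At stake is whether the protocol can deliver the first thing it says it will find out about patients. A later analysis plan cannot repair this, because it cannot recover the symptom status of people for whom it was never recorded.

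**Working it through.** **Step 1. Patients per site.** Section 3.1 gives alpha 0.05, power 80%, standardised effect 0.78, 26 per group and 20% for attrition. Two-sided normal approximation: n = 2 × (1.960 + 0.842)² / 0.78² = 2 × 7.85 / 0.608 = 25.8, rounded up to 26. Attrition: 26 / 0.8 = 32.5, rounded up to 33. The stated figures reproduce. Reading section 3.1 as 33 per group at each site gives 33 + 33 = 66 per site and 3 × 66 = 198 overall. This sample size serves the WOMAC comparison; none is given for objective 2.1.

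**Step 2. What the enrolled cohort can show.** Estimated proportion = (enrolled patients who reported symptoms) / (enrolled patients). The symptom criterion makes numerator and denominator the same people:

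- per site: 66/66 = 100%
- overall: 198/198 = 100%

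The result does not depend on the true rate or on the number enrolled.

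**Step 3. Is there another source in the text?**

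- The baseline survey in section 4.3 is a stage of the same six-month study.
- Table 8 lists initiation, intervention and follow-up, with no survey phase.
- The baseline form in section 9.1 carries an enrolment/follow-up date. Its symptom section asks for the type of symptom and a severity rating, with no yes/no item for presence.
- Section 3.2 describes consecutive screening, which could supply a denominator, but nothing requires symptom status to be kept for everyone screened.

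**Step 4. What a screening denominator would give.** The protocol states no prevalence, so p is an assumption taken over a wide range. To find 66 symptomatic patients at a site, about n = 66/p must be screened, ignoring other exclusions and refusals. Half-width of the 95% interval = 1.96 × √(p(1 − p)/n).

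| Assumed p | Screened per site, 66/p | Half-width (percentage points) |
|---|---|---|
| 20% | 330 | 4.3 |
| 35% | 189 | 6.8 |
| 50% | 132 | 8.5 |
| 65% | 102 | 9.3 |
| 80% | 83 | 8.6 |

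Example at p = 0.5: n = 66/0.5 = 132, and 1.96 × √(0.25/132) = 0.085.

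Other exclusions and refusals would raise n, so these are minimum screening numbers. Because screening stops when the target is enrolled, n is itself random and the fixed-n interval is approximate.

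**The case against.** The strongest reply is that objective 2.1 may never have been meant for the randomised cohort. It is listed apart from 2.2, only 2.2 is described as a randomised study, and 2.1 pairs symptom frequency with a nurse survey whose respondents are not trial patients. The baseline form also offers answers that an eligible patient could not give, such as Stage IV, although metastatic disease is excluded. The flowchart (Figure 3) was not available to check, so a survey step there cannot be ruled out. What stands is that a wider survey may have been intended. What does not follow is that the protocol provides one: its text gives no population, sampling frame or size for it. The 100% is accordingly a statement about enrolled patients, the only patients defined.

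A second reply is that current incidence is loose wording for prevalence. That is plausible, but the prevalence among enrolled patients is fixed by the same rule.

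A reader might go further and infer that every percentage from the baseline form is meaningless, that all of objective 2.1 fails, or that a planned comparison of cities is lost. The protocol does not support these readings. The criterion requires only some symptom. The form scores hand and knee/hip pain, stiffness and function separately, and those distributions can vary between sites, though they remain conditional on having reported symptoms. The nurse half of 2.1 has its own questionnaire (section 9.5). Objective 2.1 states no formal comparison of frequencies between cities.

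**Conclusion.** The point holds for the patient half of objective 2.1. Among enrolled patients the any-symptom proportion is 100% at each site by construction, and new onset cannot be estimated. This rests on the enrolled cohort being the only patient population defined, which is what the text shows.

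The consequence is limited. The randomised WOMAC comparison, its sample size, the nurse KAP survey and the description of symptoms among symptomatic patients are untouched. This should be fixed so that the trial can answer its own stated objective; it does not threaten the primary comparison. The screening figures of about 330 to 83 per site, with half-widths of about 4 to 9 points, illustrate what the repair could yield under assumed prevalences of 20% to 80%. They do not measure harm in the present plan.

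**What to change.** 1. In the consecutive screening already described in section 3.2, log every patient who has been on an aromatase inhibitor for at least 6 months. Record whether she has musculoskeletal symptoms (yes/no), in the terms of the entry criterion, before that criterion is applied.
2. Report symptomatic/screened at each site with a 95% confidence interval. State whether patients who meet another exclusion or decline the trial are counted in the denominator.
3. In objective 2.1, replace incidence with prevalence among patients on an aromatase inhibitor for at least 6 months.
4. If no such log will be kept, reword only the patient half of 2.1 as a description of the type, location and severity of symptoms in symptomatic patients. Keep the nurse KAP half as it is.
5. If a separate patient survey is intended, define its population, sampling and size in the protocol.

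The cost of items 1 to 3 is one entry on a screening log, a small clerical load at screening and one reworded objective. Eligibility, treatment and the trial's sample size do not change.

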3.3 Allocation Concealment

To prevent allocation bias, this study uses an allocation concealment technique. The randomization sequence will be managed by an independent third party, ensuring that the clinical research team is unaware of patient group assignments prior to allocation. In practice, the randomization results will be sealed in opaque envelopes, which will be opened by independent personnel after each patient's enrollment to determine group allocation. This blinding method minimizes potential bias and interference during study implementation.

4. Intervention Plan

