4.5 Intervention Strategies

In this study, all research centers provide the same symptom management materials, but each center uses different media formats based on local resources and cultural context.

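### Allocation is described as simple, with no stratification or blocking by site, although each of three differing sites has a target of 33 patients per arm

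*Protocol*

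**What the plan says.** - Protocol section 3 (Research Design): "This study employs a simple randomized controlled trial (RCT) design".
- Section 3.2: consecutive patients "will be enrolled sequentially during the study period until the predetermined sample size is reached", and each is assigned "to either the intervention or control group based on a computer-generated random sequence".
- Section 3.3: an independent third party manages the sequence, "the randomization results will be sealed in opaque envelopes", and independent personnel open them after enrolment.
- Section 3.1: the calculation ends "resulting in a total of 33 patients per group", followed by "Each research site will thus recruit 33 patients for both the intervention and control groups". The natural reading is 33 per arm at each site, so 66 per site and 198 over the three sites listed in 4.4.1.
- Section 4.5: the materials are common to all sites, but "each center uses different media formats based on local resources and cultural context". Shanghai and Dali use the app (4.5.1). Jakarta receives the same content offline (4.5.2).
- Section 4.2.2: the same two or three staff recruit, deliver the intervention and follow up.

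The protocol mentions no stratification, blocking, minimisation or site-specific list.

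**The concern.** A fixed number per arm at each site and an unrestricted sequence do not fit together. Simple allocation leaves the arm sizes at a site to chance, so the section 3.1 target would be met only by luck or by some unstated end-of-recruitment rule.

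Site is the obvious factor to balance. The sample size is set per site, objective 2.2 concerns effectiveness across cultural contexts, and the sites span two countries and two media. If the arms are unevenly spread over sites, a crude pooled comparison carries part of any difference between sites, and the site-level comparisons become lopsided. Filling the quota by closing an arm would also make the last assignments at that site certain, and sealed envelopes cannot hide a certain outcome.

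**Working it through.** **Inputs.** Section 3.1 gives a standardised effect of 0.78, alpha 0.05, power 80%, 20% attrition and 33 per arm per site. Section 4.4.1 gives three sites. The 1:1 ratio is implied by the equal targets.

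**The plan's own figure.** With a two-sided normal approximation, n per arm = 2(1.96 + 0.8416)² / 0.78² = 25.8, rounded up to 26. Then 26 / (1 − 0.20) = 32.5, rounded up to 33. Both stated figures reproduce.

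**Split at one site under unrestricted 1:1 allocation.** The intervention count is Binomial(66, 0.5).
- SD = √(66 × 0.25) = 4.1; central 95% range 25 to 41.
- P(exactly 33:33) = C(66,33) / 2⁶⁶ = 0.0978. At all three sites: 0.0978³ = 0.0009.
- P(38:28 or worse, either way) = 2 × P(X ≤ 28) = 0.268. At least one site of three: 1 − (1 − 0.268)³ = 0.607.
- If a single list of 198 happened to end 99:99, P(33:33 at every site) = C(66,33)³ / C(198,99) = 0.017.

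**Power cost at one site.** Two-sided t-test, effect 0.78, 20% lost from each arm:

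| Randomised split | Power |
|---|---|
| 33:33 | 79.4% |
| 28:38 | 78.5% |
| 25:41 | 76.9% |
| Average over Binomial(66, 0.5) | 78.8% |

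The average loss is 79.4 − 78.8 = 0.6 points.

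**Size of the mixing in a crude pooled comparison (illustration).** Suppose Jakarta splits 38:28 and the other two sites 33:33. The arms are then 104 and 94, and Jakarta's share is 38/104 = 0.365 in one arm against 28/94 = 0.298 in the other. The unadjusted arm difference moves by about 0.07 of whatever gap in mean WOMAC exists between Jakarta and the Chinese sites.

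**Two ways of forcing the target, neither stated in the protocol.**
- Close an arm at 33. The expected number of allocations left when the first arm fills is 66 × 0.0978 = 6.5. Simulation of 200,000 runs gives 6.46, with 5th to 95th percentile 1 to 14.
- Recruit until both arms reach 33. The expected number is 66 + 6.5 = 72.5. Simulation gives 72.4, with 90th percentile 80, against the planned 66.

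**The case against.** The strongest reply is that *simple* may describe a plain two-arm trial rather than the allocation method. The protocol is silent on stratification but does not exclude it, and a per-site target would suit balanced per-site lists equally well. This stands as a limit on the claim: the document does not provide for site stratification, but it cannot be said to have rejected it. The correction to the text is the same on either reading.

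A reader might infer that concealment is already broken. The documents do not support that. No rule closes an arm at 33, section 3.2 lets a site stop at 66 with unequal arms, and section 3.3 has sound safeguards. The predictable allocations arise only if a site caps an arm.

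A reader might also infer a serious loss of power. At the protocol's effect of 0.78 with 3 × 26 = 78 completers per arm, pooled power is about 99.8%. Even if site explained 30% of the variance (an assumption) and the analysis ignored site, the effect would shrink to 0.78 × √0.7 = 0.65 and power would be about 98%. Such a loss would in any case come from the analysis, which the unseen SAP may settle, and not from the randomisation.

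Finally, chance imbalance under valid randomisation does not bias the estimate in expectation, and adjustment for site can deal with it. That is also right. By the same figures, 73% of sites would be less uneven than 38:28. The intervention content does not differ between sites, and the contrast in medium is Jakarta against the two Chinese sites only.

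**Conclusion.** The point holds in a limited form. As written, the allocation scheme does not deliver the target of 33 per arm at each site and leaves the arms free to fall unevenly over sites that differ in country and partly in medium. If allocation is unrestricted 1:1 with 66 patients per site, about one site in ten meets the target exactly, and there is a 61% chance that at least one site is 38:28 or worse.

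The consequence is avoidable imbalance by site, with a power cost of about 0.6 points at a single site. It is not bias in expectation and not a demonstrated breach of concealment. The concealment risk is conditional on an unstated capping rule. It deserves mention because the staff who recruit also deliver the intervention and could count how many patients each arm has. The case for change is that a better scheme costs almost nothing and matches the per-site target and the cross-cultural objective.

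**What to change.** In sections 3.2 and 3.3, replace the simple scheme with 1:1 permuted-block randomisation stratified by site. Block sizes should vary and not be disclosed to the sites, and the independent third party should hold a separate numbered envelope series for each site. In section 3, remove or define the word *simple*. This gives 33:33 at each site when the blocks complete, and otherwise keeps each arm within half a block of its target. No arm needs to be closed and no extra patients are needed.

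Any pooled WOMAC comparison should then include site as the stratification factor. If the SAP already does so, only the randomisation text needs to change.

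The cost is one list per site, with no extra staff and no change for patients. It has to be settled before the first patient is randomised.

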3.1 Sample Size

The primary measurement tool for this study is the Western Ontario and McMaster Universities Osteoarthritis Index (WOMAC), used to assess aromatase inhibitor-related musculoskeletal symptoms in breast cancer patients. The sample size estimation is based on effect size and standard deviation data from previous studies, with a significance level of $\alpha=0.05$ and a statistical power of 80%. The calculated effect size is 0.78. Based on these parameters, each group requires 26 patients, with an additional 20% to account for potential attrition, resulting in a total of 33 patients per group.

Each research site will thus recruit 33 patients for both the intervention and control groups.

3.2 Sampling Method

Patients will be screened and recruited on a consecutive enrollment basis, meaning that all patients meeting the inclusion criteria will be enrolled sequentially during the study period until the predetermined sample size is reached.

Upon enrollment, each patient will undergo a comprehensive baseline assessment, and the research team will ensure that patients understand the study's details and voluntarily sign informed consent forms. After enrollment, patients will be assigned

to either the intervention or control group based on a computer-generated random sequence. The intervention group will receive a management program for musculoskeletal symptoms, while the control group will receive standard care.

3.3 Allocation Concealment

To prevent allocation bias, this study uses an allocation concealment technique. The randomization sequence will be managed by an independent third party, ensuring that the clinical research team is unaware of patient group assignments prior to allocation. In practice, the randomization results will be sealed in opaque envelopes, which will be opened by independent personnel after each patient's enrollment to determine group allocation. This blinding method minimizes potential bias and interference during study implementation.

4. Intervention Plan

4.1 Intervention Objectives

4.1.1 Patient Outcomes

- **Target Population:** Patients undergoing endocrine therapy following early-stage breast cancer surgery.
- **Intervention Duration:** The intervention will last for 6 months, with regular follow-up and symptom assessment.
- **Expected Outcomes:** Through intervention, patients' musculoskeletal symptoms (e.g., pain, stiffness) are expected to significantly improve, with a corresponding improvement in quality of life.

